4.2 SAFETY ANALYSIS SET

Safety analysis set is the same as the full analysis set.

4.3 OTHER ANALYSIS SET

There are no other analysis sets to be used in this study

4.4 SUBGROUPS

Subgroup analysis will not be performed.

5 ENDPOINTS AND COVARIATES

For the untreated group, baseline value is defined as the value recorded at the date of informed consent, whereas for the treated group the baseline value is the value taken at Day 1.

5.1 EFFICACY/EFFECTIVENESS ENDPOINT(S)

For objective #2, these are the following endpoints:

UUUUUUUUUU	
Anthropometric endpoints	• Z-score of standing height
	• Arm span to height/length difference.

5.2 SAFETY ENDPOINTS

Not applicable.

PFIZER CONFIDENTIAL CT24-WI-GL03-RF03 2.0 Non-Interventional Statistical Analysis Plan For Secondary Data Collection Study 01-Jun-2020 Page 10 of 17

5.3 OTHER ENDPOINTS

Not applicable.

5.4 COVARIATES

Not applicable.

6 HANDLING OF MISSING VALUES

No imputation for missing values will be performed.

7 STATISTICAL METHODOLOGY AND STATISTICAL ANALYSES

7.1 STATISTICAL METHODS

Descriptive statistics will be tabulated on patient demographic and baseline clinical characteristics between achondroplasia patients from Study C4181005 and patients from Study C4181001 who meet all the inclusion and exclusion criteria of Study C4181005.

7.2 STATISTICAL ANALYSES

To evaluate objective 2, mixed-effect, repeated measures (MMRM) models will be used. The fixed effects of treatment, visit, treatment-by-visit interaction, age and gender will be included. Visit will be modeled as a categorical covariate. (If the model does not converge then Visit will be modeled as a continuous covariate.) There will be random effects for both slopes (i.e. visit as a continuous variable) and intercept, clustered by subject nested within a propensity-score matched set or clustered by subject weighted by Inverse Probability Weights (see section 10.3). Random effects for slopes will be removed in the above models do not converge. Unstructured covariance matrix will be assumed for the model errors.

7.2.1 Objective 1

To construct a concurrent external control for Study C4181005, a propensity score (PS) will be created to achieve balance across covariates between achondroplasia patients from Study C4181005 and patients from Study C4181001 who meet all the eligibility criteria of Study C4181005. The PS will be estimated using standard logistic regression approaches with the "outcome" variable being the data source (whether patients were included in Study C4181005 and exposure to recifercept treatment) and the predictors being the variables associated with both the exposure (recifercept treatment) and the outcomes of interest (i.e. standing height & arm-span-to-height difference). This model will provide the predicted probability of being in the trial cohort relative to the concurrent external control cohort as a function of the covariates (the propensity score of being included in Study C4181005). The potential covariates may include demographics (e.g. age, gender, race and ethnicity), clinical characteristics (e.g. presence of achondraplasia-related complications, Tanner stage, and other non-achondroplasia-

PFIZER CONFIDENTIAL

CT24-WI-GL03-RF03 2.0 Non-Interventional Statistical Analysis Plan For Secondary Data Collection Study 01-Jun-2020 Page 11 of 17 related conditions of medical significance). The distribution of the PS will be reviewed and patients with a PS in the areas of nonoverlap and/or with extreme PS values might be excluded to improve validity (PS trimming). Each patient in the PS trimmed receifercept group will be matched on a ratio of 1:1 with patients in the PS trimmed concurrent external control using optimal nearest neighbour matching with a maximum caliper of 1%. Pre- and post-matching balance will be assessed using standardized differences between these two PS-matched groups. A negative control outcome may also be identified to evaluate the pre- and post-matching balance. There are different options that will be considered while modelling via PS. These include:

- 1. Calipers: range from [.01,.25]
- 2. Statistic (used to match treated to control subject): logit of PS, minimizing difference of PS, Mahalanobis distance
- 3. Ratio match (treatment-to-untreated): 1-to-1, 1-to-m

Exact matching can be included within the PS model. Exact matching will be done by gender. A binary variable will be created to specify race. The variable will have the value of "Yes" for "White" and "No" for all other values.

Standardized mean differences of the matched variables are the main criteria used to determine whether objective 1 is met. An external control dataset is confirmed (i.e., objective 1 is met) when all of the standard mean differences for the matched variables are less than 0.1.

After the concurrent external control is constructed by PS matching, descriptive statistics will be tabulated on patient demographic and baseline clinical characteristics between achondroplasia patients from PS-matched recifercept phase 2 trial cohort and those from PS-matched concurrent external control. Two-sample T-tests will be used for continuous variables, and chi-square tests for categorical variables assuming the distribution is normal. Frequency of primary, secondary and exploretary outcomes of interest and 95% confidence intervals will be computed.

Another method to construct an external control for C4181005 for the purpose of estimating the Average Treatment Effect (ATE) of recifercept is Inverse Probability Weights (IPW). IPW will use PS to weight the observations prior to the analysis of height growth. Weights are calculated for each subject as 1/PS for Recifercept and 1/(1-PS) for the untreated group. Standardized differences between the untreated and Recifercept groups will be assessed both before and after weighting. Standardized mean differences of <10% may be considered a negligible difference.

7.2.2 Objective 2

Achondroplasia disease measures including height growth, anthropometric measurements, difference in functional status and health-related of life will be summarized using descriptive statistics.

Analyses of Height Z-Score and Arm-Span-to-Height Difference

If objective 1 is met, either a matched dataset – exclusively with a ratio of treated to untreated of 1:1 - via PS or a dataset augmented by IPW will be used to analyze height Z-Score. Baseline summaries of Height Z-score and Arm-Span to Height-difference and change from baseline a months 3, 6, 9, and 12 will be presented.

7.2.3 Safety Analyses

Not applicable.

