10.3 APPENDIX 3: DIAGNOSIS AND PROCEDURE CODES USED IN THE STUDY

Propensity Score Matching

proc psmatch data = adsl ;

class SEX DRUG WHITE ;

psmodel DRUG (treated = 'Recifercept') = SEX AAGE WHITE ;

match method = varratio (kmax = 4) distance = lps exact = (SEX WHITE);

assess lps allcov / weight = none plots = (barchart boxplot);

```
output out(obs = match) = outasa lps = _Lps matchid = _MatchID ;
```

run;

PFIZER CONFIDENTIAL

CT24-WI-GL03-RF03 2.0 Non-Interventional Statistical Analysis Plan For Secondary Data Collection Study 01-Jun-2020 Page 16 of 17

MMRM with Propensity Score Matching clusters

```
proc mixed data = ps_match_mmrm ;
    by paramcd ;
    class _MatchID usubjid sex drug (ref = 'Not Treated') ;
    model chg = month drug / s ; /*** s = Solution for Fixed Effects ***/
    random int month / subject = usubjid(_MatchId) ;
run ;
```

Inverse Probability Weighting

```
proc psmatch data = adsl region = allobs ;
    class SEX DRUG WHITE ;
    psmodel DRUG (treated = 'Recifercept') = SEX AAGE WHITE ;
    assess lps var = (SEX AAGE WHITE) / weight = atewgt plots = (barchart boxplot) ;
    output out(obs = all) = ipw_ate ATEWGT = _ATE_ ;
```

run;

MMRM with Inverse Probability Weights

```
PROC GLIMMIX DATA = ate_ipw METHOD = quadrature (qpoints = 27) EMPIRICAL =
classical NOREML ;
NLOPTIONS GCONV = 1E-10 TECHNIQUE = TRUREG ;
where PARAMCD APSBLFL = "Y" ;
CLASS DRUG (REF = "Not Treated") USUBJID ;
MODEL CHG = DRUG MONTH / SOLUTION ;
RANDOM INT MONTH / subject = USUBJID WEIGHT = _ATE_ ;
```

RUN;

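### The Objective 2 outcome model analyses change from baseline without the baseline value of the endpoint, and SAP 5.4, 7.2 and 10.3 disagree on its other terms

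*SAP*

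**What the plan says.** The SAP 3.1 hypothesis concerns mean change from baseline in height Z-score up to 12 months. SAP 5.1 adds arm-span-to-height difference, and 7.2.2 presents both endpoints as change at months 3, 6, 9 and 12.

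- **Model text (SAP 7.2):** "The fixed effects of treatment, visit, treatment-by-visit interaction, age and gender will be included".
- **Covariates (SAP 5.4):** "Not applicable".
- **Outcome program, matched data (SAP 10.3):** "model chg = month drug / s". Sex is in the CLASS statement but not in MODEL.
- **Outcome program, weighted data (SAP 10.3):** "MODEL CHG = DRUG MONTH / SOLUTION".
- **Propensity programs (SAP 10.3):** both use "psmodel DRUG (treated = 'Recifercept') = SEX AAGE WHITE", and the matching program adds "exact = (SEX WHITE)".
- **Propensity text (SAP 7.2.1):** an open list, "The potential covariates may include demographics (e.g. age, gender, race and ethnicity), clinical characteristics" and so on, which does not name the baseline value of either endpoint.
- **Balance rule (SAP 7.2.1):** Objective 1 is met when the standardised mean differences of the matched variables are all below 0.1.
- **Baseline (SAP 5):** taken at informed consent for the untreated group and at Day 1 for the treated group. SAP 7.2.2 summarises baseline endpoint values descriptively.

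**The concern.** The groups are not randomised, so their baseline height Z-score and arm-span difference may differ. With the programs as written, no step limits that difference. The propensity score contains sex, age and White or not, the 0.1 rule applies to matched variables only, and the outcome model has no baseline term. Objective 1 could be declared met with a clear imbalance in the very quantity from which change is measured. A change score subtracts the baseline level, but not the part of later change that depends on that level. It is also less precise than a baseline-adjusted contrast when the correlation with follow-up is below 1.

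The conflict between sections matters separately. An analyst following 7.2 fits age, gender and treatment-by-visit; one following 10.3 fits none of them. The choice matters most for arm-span-to-height difference, a raw difference with no standardisation for age or sex.

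**Working it through.** **Where the baseline value could enter**

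| Step | Terms present | Baseline endpoint value |
|---|---|---|
| Propensity text, 7.2.1 | open list | not named, not excluded |
| Propensity programs, 10.3 | sex, age, White | absent |
| Balance rule, 7.2.1 | matched variables | not covered by the programs' variables |
| Outcome text, 7.2 | treatment, visit, interaction, age, gender | absent |
| Outcome programs, 10.3 | drug, month | absent |

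**The plan's own figure.** The only sample-size figure is Protocol Table 1, for a median ratio. Its first cell, 88 pairs (type I error 0.05, power 0.8, ratio 1.5), is reproduced by (pi/2)^2 x (2.128 + 0.842)^2 / 0.5^2 = 87.04, rounded up. Here 2.128 is the normal quantile at 1 - 0.05/3, an inferred split that the documents do not state. This calculation has no baseline term and does not bear on the present point.

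**Inputs.** From the documents: two-sided alpha 0.05 (SAP 3.2) and 1:1 matching (SAP 7.2.2). Assumed, because the documents give no value: baseline-to-follow-up correlation rho of 0.7 to 0.95, residual baseline difference d of 0.3 or 0.1 SD, equal SDs, and 54 pairs. The documents give 54 only as the planned number of trial participants aged 2 to 10 years. They also give 63 trial participants in all and, in Protocol 9.6, about 30 pairs at the first data release.

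**Bias.** If both groups regress to one common mean, the slope of change on baseline is rho - 1. With no treatment effect, the unadjusted contrast then moves by (1 - rho)d in size, opposite in sign to the imbalance.

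**Standard error** of the change contrast, in baseline SD units: sqrt(4(1 - rho)/54).

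**Rejection rate:** P(|Z + shift| > 1.96), where shift = bias/SE.

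| rho | d | Bias (SD) | SE | Shift | Rejection |
|---|---|---|---|---|---|
| 0.70 | 0.3 | 0.090 | 0.149 | 0.60 | 9.2% |
| 0.95 | 0.3 | 0.015 | 0.061 | 0.25 | 5.7% |
| 0.70 | 0.1 | 0.030 | 0.149 | 0.20 | 5.5% |
| 0.95 | 0.1 | 0.005 | 0.061 | 0.08 | 5.1% |

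**Precision.** The variance ratio of adjusted to change-score contrast is (1 + rho)/2. The SE ratio is sqrt(0.85) = 0.922 at rho 0.7 and sqrt(0.975) = 0.987 at rho 0.95, a gain of 7.8% and 1.3%. This assumes balanced baselines. At d = 0.3 the adjusted variance grows by 1 + d^2/4 = 1.0225, so the ratios become sqrt(0.85 x 1.0225) = 0.932 and sqrt(0.975 x 1.0225) = 0.998.

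**Simulation check under a common mean** (63 per group, 4,000 runs per scenario). At rho 0.80 and d = 0.5 the unadjusted contrast was shifted by -0.099 SD and rejected at 14.0% (formula: 14.4%). At rho 0.90 and d = 0.1 it rejected at 5.2%. With the baseline term added, bias was below 0.002 SD and rejection was 4.4 to 5.3% in all five scenarios run.

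**The case against.** The strongest case against is that baseline adjustment is not automatically safer in non-randomised groups. If the groups differ by a stable amount that persists without treatment, the change score is unbiased and adjustment creates the error. In a simulation with 54 per group, a stable 0.3 SD difference, no treatment effect and 5,000 runs, the change score rejected at 5.0% at rho 0.7. The adjusted model was biased by 0.088 SD and rejected at 9.8%. At rho 0.95 the figures were 4.9% and 5.6%. The documents do not settle which situation applies. This stands, and it is the reason to keep the unadjusted analysis. It does not remove the case for adjustment: SAP section 2 says all trial patients were recruited from the natural history study, which makes a common mean plausible.

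Three stronger readings are tempting, and the documents do not support them.

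- **That the programs carry no covariates.** The propensity programs use sex, age and White, with exact matching on sex and White. Only the outcome MODEL statements are bare.
- **That baseline differences pass whole into the treatment effect.** Change already subtracts the level; at most the (1 - rho) part remains, and only under a common mean.
- **That inflated type I error is established.** rho, d and the number of pairs are assumptions, the formula is for a single visit while the plan is a repeated-measures model, and shared eligibility criteria may keep d small.

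It can also be said that SAP section 1 records the removal of age and gender from 5.4 as deliberate. That explains 5.4 but leaves 7.2 unaltered, so the conflict remains. With exact matching on sex, a sex term adds little against confounding by sex in the matched analysis; the weighted analysis has no exact matching. Finally, the open propensity list could admit baseline height, and the descriptive summaries would show an imbalance. Neither is a commitment to act on one.

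**Conclusion.** The omission is certain: no text or program adjusts change for the baseline value of the endpoint, and nothing in the programs balances it. The conflict among 5.4, 7.2 and 10.3 is also certain, and the plan cannot be run as written until it is resolved.

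The consequence is conditional and moderate. It rests on a common mean, equal SDs and the assumed rho, d and 54 pairs. The excess over 5% is between 0.7 and 4.2 percentage points at an imbalance of 0.3 SD, and at most about half a point at 0.1 SD. The precision gain is modest, and smaller still where the baselines differ. This is worth correcting because the correction is cheap, not because a large bias has been shown.

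**What to change.** 1. Add the baseline value of the analysed endpoint, and baseline-by-visit, to the fixed effects in SAP 7.2 and to both outcome MODEL statements in 10.3.
2. Report the standardised mean difference of that baseline value after matching and after weighting, beside the matched variables.
3. Make 5.4, 7.2 and 10.3 agree. List baseline, age and sex in 5.4, keep age and sex in the outcome model (particularly for arm-span-to-height difference), and put treatment-by-visit into the programs if 7.2 stands.
4. Keep the unadjusted change-score model as a named sensitivity analysis. State that the adjusted model assumes no stable difference between the groups, and the unadjusted one no dependence of change on baseline.

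The cost is SAP wording, two MODEL statements, a slightly larger model and one extra sensitivity analysis. No new data are needed, and the baseline term excludes no child, because every change value already requires a baseline.

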9.3. Variables

Table 3. Listing of all variables of importance

Variable	Role	Phase II Recifercept Clinical Trial (C4181005)	Natural History Study (C4181001)	Operational definition
Achondroplasia treatment	Exposure	Recifercept dosage and duration: Recifercept dosage: 1mg/kg once-weekly 2mg/kg twice-weekly 1.5mg/kg once-daily	Achondroplasia-related treatment and duration Collected every 3 months	
Height Growth	Primary outcome	Collected every 3 months until end of study participation	Collected every 3 months until end of study participation	Defined as increase in height growth above expected growth in reference population, defined as the height growth in the achondroplasia reference population +50%
Anthropometric Measurements	Secondary outcome	 Standing height Sitting height Knee height Arm span Length of the legs Sitting height/standing height ratio Arm span to height/length difference knee height: lower segment ratio Collected at 1m, 3m, 6m, 9m, 1y 	 Standing height Sitting height Knee height Arm span Length of the legs Sitting height/standing height ratio Arm span to height/length difference knee height: lower segment ratio -collected at baseline, every 3m, and end of study visit 	Length of the legs will be calculated as the difference between standing and sitting height
Achondroplasia- related orthopaedic complications	Secondary outcome	Baseline collection - foramen magnum decompression - cranial surgery Occurrence during follow-ups	 Lordosis Kyphoscoliosis Small foramen magnum Spinal stenosis collected at 6m, 1y, 2y, 3y, and 4y Collected every 3 months until end of study participation 	

PFIZER CONFIDENTIAL CT24-WI-GL02-RF02 3.0 Non-Interventional Study Protocol Template For Secondary Data Collection Study 23-May-2022 Page 19 of 26

Other achondroplasia- related complications	Secondary outcome	 Sleep disordered breathing Acute Otitis Media (AOM) Hydrocephalus 	 Sleep disordered breathing Acute Otitis Media (AOM) Hydrocephalus 	
CCI				
Demographics	Covariate	- Age	- Age	
		- Gender - Race and ethnicity	- Gender - Race and ethnicity	
		Collected at baseline	Collected at baseline	
Puberty	Covariate	Tanner stage	Tanner stage	
		Collected at baseline	Collected at baseline	
Weight	Covariate	Body weight	Body weight	
		Collected every 3 months until end of	Collected every 3 months until end of	
		study participation	study participation	
History of	Covariate	Sleep-disordered breathing	Sleep-disordered breathing	

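### SAP 7.2 gives each child both random intercepts and slopes and unstructured errors; the covariance split is not identifiable, and the first fallback drops visit-specific contrasts without curing it.

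*SAP*

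**What the plan says.** SAP 7.2 sets out the Objective 2 model in one paragraph.

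- **Mean model:** "The fixed effects of treatment, visit, treatment-by-visit interaction, age and gender will be included". Visit is categorical in the first instance.
- **Random effects:** "There will be random effects for both slopes (i.e. visit as a continuous variable) and intercept". Their level is "clustered by subject nested within a propensity-score matched set or clustered by subject weighted by Inverse Probability Weights". In both versions the unit is the child.
- **Errors:** "Unstructured covariance matrix will be assumed for the model errors".
- **First fallback:** "If the model does not converge then Visit will be modeled as a continuous covariate".
- **Second fallback:** "Random effects for slopes will be removed in the above models do not converge". The SAP does not say whether visit returns to categorical at this step.

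SAP 7.2.2 fixes the post-baseline visits: "change from baseline a months 3, 6, 9, and 12 will be presented". For the trial arm, Protocol 9.3 (Table 3) also lists a one-month anthropometric visit: "Collected at 1m, 3m, 6m, 9m, 1y".

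The programs in SAP 10.3 differ from this text. Both the matched and the IPW program have a random intercept and month effect per child and no residual covariance structure. Month is not a class variable, and there is no treatment-by-visit, age or gender term.

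**The concern.** An unstructured error matrix is already the most general covariance for a child's repeated measurements. A random intercept and slope for the same child only describe part of that matrix a second time. The data can estimate the sum of the two layers but cannot divide it between them.

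The redundancy would be only untidy if the fallback removed it. Instead, the first response to a convergence failure changes the mean model. Making visit continuous turns the treatment-by-visit term into a straight line, so the separate treatment contrasts at months 3, 6, 9 and 12 are lost over a problem in the covariance part. The second response leaves one layer of redundancy. The SAP also does not say whether a singular-Hessian warning at a finished fit counts as non-convergence, so two analysts could follow the text and report different models for the one hypothesis in SAP 3.1.

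**Working it through.** The documents give no figure for this point, so the check is of identifiability.

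**Inputs.** T = 4 visits (SAP 7.2.2); unstructured errors R, random intercept and slope G, both per child (SAP 7.2). The structure of G is not stated, so both options are shown: two variances, or two variances plus a covariance.

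**Formula.** A child's covariance matrix is V = ZGZ' + R, with Z = [1, month]. V has T(T+1)/2 distinct elements, so 4 × 5 / 2 = 10. The model is identifiable only if the number of covariance parameters equals the rank of the Jacobian of those elements.

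| Specification (T = 4) | Parameters | Rank | Surplus |
|---|---|---|---|
| SAP 7.2, G with covariance | 3 + 10 = 13 | 10 | 3 |
| SAP 7.2, G with variances only | 2 + 10 = 12 | 10 | 2 |
| After fallback 1 (visit continuous) | 13 or 12 | 10 | 3 or 2 |
| After fallback 2 (slopes removed) | 1 + 10 = 11 | 10 | 1 |
| Unstructured errors alone | 10 | 10 | 0 |
| Random effects, independent residuals, G with covariance | 3 + 1 = 4 | 4 | 0 |
| Random effects, independent residuals, variances only (as in 10.3) | 2 + 1 = 3 | 3 | 0 |

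With the month 1 visit, T = 5 and V has 15 distinct elements. The counts become 18, 17 and 16 against rank 15, with the same surpluses of 3, 2 and 1.

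**What stays identified.** On one simulated dataset (30 children per group, illustrative variances), four different splits of the same V, including G = 0, gave the same log-likelihood (41.7600), the same Month 12 treatment estimate (0.0958) and the same standard error (0.1080). The likelihood is flat across the splits, but the treatment effect and its precision do not depend on the split.

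**What fallback 1 can do to visit-specific effects.** The treatment effects in Z-score units are assumed. An unweighted least-squares line is fitted through the four values. The mean month is 7.5, the deviations are −4.5, −1.5, 1.5 and 4.5, and their sum of squares is 45. The Month 12 value is the mean effect + 4.5 × slope.

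- Linear, 0.025/0.05/0.075/0.10: mean 0.0625, slope 0.375/45 = 0.00833, Month 12 = 0.0625 + 0.0375 = 0.100. Error 0%.
- Plateau, 0.05/0.10/0.10/0.10: mean 0.0875, slope 0.225/45 = 0.005, Month 12 = 0.0875 + 0.0225 = 0.110 against 0.10. Error 10%.
- Rise and fall, 0.05/0.10/0.10/0.05: mean 0.075, slope 0, Month 12 = 0.075 against 0.05. Error 50%.

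The real fit would weight by the estimated covariance. Under a range of assumed AR(1)-type and random-walk covariances, the plateau gives 0.100 to 0.116 and the rise and fall 0.050 to 0.082. The error therefore ranges from none to about 60% and shrinks as the within-child correlation rises.

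**The case against.** The strongest reply has four parts.

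1. **The treatment effect is identified.** A reader might infer from the parameter count that the Objective 2 effect cannot be estimated. That is wrong. With G = 0 the SAP model is the ordinary unstructured MMRM, and every other split gives the same estimate and standard error. This part stands in full.

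2. **Non-convergence is not certain.** A reader might infer that the fit must fail. A singular information matrix is unavoidable, but a flat ridge does not oblige an optimiser to stop. In 100 simulated datasets (30 children per group, four complete visits, illustrative variances), a quasi-Newton fit of the 13-parameter covariance reached the maximum in all 100, as did unstructured errors alone. That was not PROC MIXED and had no missing visits, so failure remains a risk. This part stands to that extent.

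3. **The code fits something else.** SAP 7.2 refers to 10.3, where the programs have random effects only and are identifiable. This limits the practical effect of the redundancy but does not rescue the text. The programs enter month as continuous without any convergence failure and have no treatment-by-visit term, so the categorical-visit analysis of 7.2 is programmed nowhere.

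4. **Linearity is prespecified, and Month 12 is not singled out.** A reader might infer a 50% bias in a Month 12 primary contrast. SAP 3.1 speaks of change up to 12 months and names no Month 12 contrast. The linear fallback is written in the plan. The 10% and 50% figures come from chosen profiles, and a linear profile gives 0%. This part also stands.

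None of the four answers the narrower point: the text describes one covariance twice, and neither fallback removes the duplication.

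**Conclusion.** The point holds in a limited form. The model in SAP 7.2 is over-parameterised by 2 or 3 covariance parameters as written and by 1 after both fallbacks, whatever the number of visits. The treatment and treatment-by-visit effects are identified, and a converged fit is usable. The practical fault is the order of the fallbacks: a possible covariance failure is met by giving up visit-specific contrasts, at a cost of anywhere from nothing to a material distortion depending on the unknown shape of the effect over time.

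This assumes that the model errors in SAP 7.2 are the within-child residuals and that the analysis visits are those in SAP 7.2.2. Because a converged fit is valid and the appended programs do not contain the redundancy, this is a should-fix, best handled together with the differences between 7.2 and 10.3.

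**What to change.** 1. **Keep one covariance description.** For example, use an MMRM with categorical visit, treatment-by-visit, age and gender, and `REPEATED visit / subject=usubjid type=UN`, with no random intercept or slope per child. Random effects with independent residuals would also remove the redundancy; either is acceptable if it is the only one. SAP 5.4 currently lists no covariates, so the age and gender terms of 7.2 should be reconciled with it in the same edit.

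2. **Replace the fallback.** Prespecify a sequence that simplifies the covariance and keeps visit categorical throughout, for example unstructured, then heterogeneous Toeplitz, then AR(1) or compound symmetry with sandwich standard errors. State what counts as non-convergence, including a non-positive-definite Hessian or G matrix.

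3. **Align the 10.3 programs.** Give the matched and IPW programs the same mean model, weighted in the IPW case.

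The cost is a rewrite of the covariance and fallback sentences in one SAP paragraph and the matching program lines. No new data are needed.
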